5.10 Interim Analyses and Data Monitoring

When all subjects have completed the Month 6 visit, effectiveness data from all subjects up to the Month 6 visit will be reviewed.

No cleaning or partial lock of

data will be performed for this data review, and no formal report will be written to summarize the review. Only subject data listings will be used together with the photographs.

The results of this interim analysis will be kept within a minimum number of persons, including the Sponsor biostatistician, clinical data analyst, clinical project manager, and approximately 3 people from the Aesthetic project leadership.

5.11 Multi-Center Studies

Study center will not be considered as an explicative factor in the statistical analyses.

5.12 Multiple Testing

Due to the proof-of-concept purpose of this trial, no alpha-level adjustment for multiplicity will be applied.

6 Summary of Study Data

6.1 Subject Disposition

The disposition of subjects will be presented in tables and/or figures as appropriate. The number and percentage of screened, treated, completed, and withdrawn subjects (including reasons for withdrawal) will be presented, as well as number of subjects in each analysis population set.

Subject disposition by study center will be tabulated.

A by-subject listing of inclusion into analysis sets and exclusion reasons, and study completion information including reason for study treatment discontinuation or early withdrawal from study, if applicable, will be presented.

All withdrawn subjects will be listed individually, including at least subject number, date and reason for withdrawal, and last visit performed, along with the relevant comments recorded on the eCRF (i.e., the Exit Form).

6.2 Screen Failures

Screen failures will be summarized by study center and inclusion/exclusion criteria not met, as appropriate.

6.3 Protocol Deviations

Subjects with CSP deviations will be listed individually, including subject number and observed deviation.

Depending on the seriousness of the deviation, subjects might be excluded from the PP population, which shall be documented prior to database lock. Since PP will be used for the primary analysis at Month 9 only, the focus will be on deviations occurring before and on Month 9 visit day, as they might compromise the primary endpoint. For this study, the protocol deviations that will exclude subjects from PP are identified (but not limited to) in Table X below.

| | Deviation |
|-------------|---|
| GENERAL | |
| | Visit out-of-window |
| | Follow-up at Month 9 after baseline performed earlier than 2 weeks before, or later than 4 weeks after the scheduled visit |
| EFFECTIVENE | SS |
| | Primary effectiveness endpoint |
| | * No baseline photo is available |
| | GAIS by treating investigator missing at Month 9 after baseline |

| | Deviation |
|-------|--|
| | Treatment |
| | * Not both thighs treated |
| OTHER | • |
| | Inclusion/exclusion criteria |
| | Violate any inclusion or exclusion criteria considered to * have substantial effect on the primary effectiveness endpoint |
| | Concomitant medication/procedures |
| | Take any prohibited concomitant medication/procedures considered to have substantial effect on the primary effectiveness endpoint |

6.3.1 Out of Window Visit Duration

When a subject performs a planned study visit outside of the protocol-specified visit windows, the subject has an out of window study visit, which is considered a type of protocol deviation for this study. Knowing a subject's Screening visit and Baseline visit and using the protocol-specified visit windowing, one can calculate a subject's target study visit window date range for each planned study visit. Then, by comparing a subject's actual study visit date to the target study visit window date range, one can calculate the days over/under the actual study visit was in relation to the target study visit date, or study visit out of window duration. The duration, in days, a study visit is out of window will be summarized overall and by visit. Duration will be split into the following below categories. Duration categories will include both days before and days after the target planned visit date.

- +/- 1-2 days
- +/-1 3-7 days
- +/- 8-20 days
- +/- 21 or more days.

The number and percentage of subjects within each out of window duration category will be presented descriptively.

6.4 Demographic and Baseline Variables

Subject demographics and other baseline characteristics measured prior to treatment will be summarized descriptively for the SAF and FAS.

Demographic variables will include the following:

- 1. Age at informed consent
- 2. Sex
- 3. Race
- 4. Ethnicity

Other baseline characteristics will include the following:

5. Weight (lbs)

- 6. Height (in)
- 7. Body mass index (BMI) (kg/m²)
- 8. CCI
- 9. Fitzpatrick Skin Type Score

A by-subject listing will also be provided.

6.5 Medical History and Concurrent Diseases

Verbatim terms on eCRFs will be mapped to preferred terms (PTs) and system organ classes (SOCs) using Medical Dictionary for Regulatory Activities terminology (MedDRA) version 24.1 or later.

Medical history and concurrent diseases will be summarized by SOC and PT for the SAF. Summaries will be ordered by descending order (based on total) of incidence of SOC and PT within each SOC. A by-subject listing will also be provided.

6.6 Prior and Concomitant Therapies

Prior therapies are defined as therapies that have been used within 30 days preceding the screening visit or within the timelines specified in the Inclusion/Exclusion criteria, and then stopped prior to the screening visit.

Concomitant therapies are defined as follows:

- any existing therapies ongoing at the time of the screening visit,
- any changes to existing therapies (such as changes in dose or formulation) during the course of the study, or
- any new therapies received by the subject since the screening visit

Prior and concomitant medications will be coded using the World Health Organization Drug Dictionary (WHO-DD) version Sept. 2021 or later and will be classified according to the default Anatomical Therapeutic Chemical (ATC) classification system code (up to 4 levels), WHO-DD Drug Name, and PT.

Prior and concomitant medications will be summarized for the SAF by the ATC Class Level 3 category (or Level 2 if there is not an applicable Level 3 category) and PT. Subjects may have more than one medication per ATC category and PT. At each level of subject summarization, a subject will be counted once if he/she reports one or more medications at that specific level. A by-subject listing will also be provided.

Prior and concomitant procedures/non-pharmacological treatments will be mapped to PTs using MedDRA version 24.1 or later.

Prior and concomitant procedures will be summarized by PT for the SAF. Summaries will be ordered by descending order (based on total) of incidence of PT. A by-subject listing will also be provided.

6.7 Study Device Exposure

Eligible subjects will receive a single regimen of Sculptra. A single regimen consists of up to three injection sessions with one-month (+2 weeks) intervals. The first treatment will be administered on Day 1/Baseline visit, the second treatment at Month 1, and the third treatment at the Month 2 visit. Sufficient amount of study product, as determined by the Treating Investigator, should be injected to achieve optimal correction, defined as the best correction that could be achieved as agreed upon by the Treating Investigator and the

subject. Treatment will stop when optimal correction has been achieved and subsequent visits will be follow-up visits. The maximum recommended dose per session is six (6) vials, three (3) vials per thigh. The maximum volume injected per thigh is up to 54 mL.

Treatment exposure will be summarized for the SAF by visit as well as in total, including number of needles used, total volume injected per thigh, injection depth, injection technique, and post-injection procedures. A by-subject, by-thigh listing will also be provided and will include additional procedure information (e.g., the use of anesthetic or ice).

7 Effectiveness Analyses

7.1 General Considerations

All effectiveness analyses will be based on the FAS as described below.

7.2 Primary Effectiveness Analyses

The 7-graded GAIS will be used to assess the aesthetic improvement of cellulite by the Treating Investigator and the subject. The Treating Investigator will assess the aesthetic improvement live by comparing to a photograph taken at the baseline visit before the first treatment. The subject will assess the aesthetic improvement by comparing a photograph taken before the first treatment at the baseline visit to a photograph from the current visit. The overall treatment area will be assessed for the right and left posterior thigh separately. The Treating Investigator and the subject will, independently of each other, respond to the question: "How would you describe the aesthetic improvement today compared to the photograph taken before treatment?" by using the respective categorical scale below.

| Rating (Treating Investigator and subject) | Description (only for Treating Investigator) |
|--|---|
| Very much improved | Optimal aesthetic result for the implant for this subject. |
| Much improved | Marked improvement in appearance from the initial condition, but not completely optimal for this subject. |
| Improved | The appearance is improved from the initial condition. |
| No change | The appearance is essentially the same as baseline. |
| Worse | The appearance is worse than the initial condition. |
| Much worse | Marked worsening in appearance from the initial condition. |
| Very much worse | Obvious worsening in appearance from the initial condition. |

Table 1. Global Aesthetic Improvement Scale

For the primary effectiveness endpoint, a responder is defined as a subject who is assessed as improved or better (Improved, Much improved, Very much improved) on the GAIS for both thighs at the same visit.

The GAIS assessment by Treating Investigator will be presented in a frequency table by visit and thigh (Left, Right). Further, a contingency table of dichotomous (at least Improved; No

change or worse) response by thigh (Left, Right, Both) will be provided for each evaluator for each visit. The proportion of responders will be presented, together with a 95% binomial confidence interval for that proportion. This result at the Month 9 visit will represent the primary effectiveness endpoint. In addition, the proportion of responders (both sides combined) over time will be visualized in a graph.

All GAIS results will be listed by subject, thigh, and evaluator.

If the PP population contains less than 90% of the FAS population, the primary analysis will be repeated using the PP population.

7.3 Secondary Effectiveness Analyses

[figure not shown]
Considering the explorative nature of the secondary endpoints, all the inferential results obtained on them will be descriptively interpreted.

7.3.1 Global Aesthetic Improvement Scale (GAIS)

The tables described in section 7.2 for the primary effectiveness endpoint at the specified visits will also be used to represent secondary effectiveness endpoint #1. The proportion of improved thighs will be presented, together with a 95% binomial confidence interval for that proportion, for each thigh separately and also for both thighs combined at Month 1, 2, 6, 9 and 12. In addition, the proportion of improved thighs (both sides combined) over time will be visualized in a graph.

Similar tables will also be presented for the GAIS assessment by subject. These tables will be used to summarize secondary effectiveness endpoint #2.

8 Safety Analyses

All safety measures will be descriptively summarized for the SAF population.

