#### 8.5.2 Secondary analysis

The GAIS assessment by the Treating Investigator will be presented in frequency tables. In addition, the proportion of improved thighs (assessed as at least improved) will be presented together with a 95% confidence interval (based on the binomial distribution). This will be done for each thigh separately and also for both thighs combined at Month 1, 2, 6, 9 and 12.

The GAIS assessment by the subject will be presented in frequency tables. In addition, the proportion of improved thighs (assessed as at least improved) will be presented together with a 95% confidence interval (based on the binomial distribution). This will be done for each thigh separately and also for both thighs combined at Month 1, 2, 6, 9 and 12.

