5.6 Derived and Transformed Data

Variables requiring calculation will be derived using the following formulas:

 Responder rate (%) regarding GAIS will be calculated as (number of subjects (or thighs) being at least improved/number of subjects reporting at the specified visit)*100.

CCI

• Time to onset of an AE will be derived as the start date minus the date of most recent treatment. If the start date is missing, it will be assumed that the AE started on the day of most recent treatment.

• Duration of an AE will be derived as the stop date minus the start date + 1. If the start date is missing, it will be assumed that the AE started on the day of most recent treatment. Completely missing stop date will not be imputed and therefore no duration will be calculated in these cases. Instead, the number of AEs that were ongoing at the end of the study will be given.

Time to return to daily activities after treatment will be derived as the subject diary date/time with the first "Yes" for "Did you feel comfortable returning to daily activities today?" minus the date/time of the corresponding treatment session injection start time, and will be represented in days. Time to feeling comfortable returning to daily activities will be calculated for each diary (treatment session) separately.

Subjects who never report feeling comfortable during each session period will have their response date and time censored at the date and time of their last diary entry in each period.

- Time to onset of pre-defined expected post-treatment events collected using subject diaries will be derived as the first recorded event date minus the date of most recent treatment.
- Days A duration expressed in days between 1 date (date1) and another later date (date2) will be calculated using the following formula: duration in days = date2 – date1 + 1
- Months A duration expressed in months is calculated as the number of days divided by 365.25/12 (approximately 30.4)
- Years A duration expressed in years is calculated as the number of days divided by 365.25
- Change from baseline Change from baseline will be calculated as: Change = post baseline value – baseline value

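### Minor: SAP 7.3.1 and protocol 8.5.2 do not say whether the combined GAIS row counts thighs or women, and the stated formula and interval suit only women

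*SAP*

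**What the plan says.** Protocol 8.5.2 says that "the proportion of improved thighs (assessed as at least improved) will be presented together with a 95% confidence interval", based on the binomial distribution, and adds: "This will be done for each thigh separately and also for both thighs combined at Month 1, 2, 6, 9 and 12". It plans this for the investigator's GAIS and again for the subject's.

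SAP 7.3.1 repeats the plan, with the proportion shown "together with a 95% binomial confidence interval for that proportion, for each thigh separately and also for both thighs combined". It adds a graph of the combined figure: "the proportion of improved thighs (both sides combined) over time will be visualized in a graph".

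The one formula for a GAIS responder rate, the same in protocol 8.4 and SAP 5.6, is "number of subjects (or thighs) being at least improved/number of subjects reporting at the specified visit", times 100. The numerator may count thighs. The denominator counts only subjects.

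SAP 7.2, on the primary endpoint, works at subject level: "a responder is defined as a subject who is assessed as improved or better" on both thighs at the same visit. It plans a table of dichotomous "response by thigh (Left, Right, Both) will be provided for each evaluator" at each visit, and a graph over time of responders with both sides combined. SAP 7.3.1 then says that the tables "for the primary effectiveness endpoint at the specified visits will also be used to represent secondary effectiveness endpoint #1".

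The secondary endpoints in SAP 3.2.3 are defined for each thigh separately. Neither document defines a combined secondary endpoint or mentions correlation between a woman's two thighs.

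**The concern.** The combined row can be read in two ways, and each leaves something to correct.

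- **Pooled thighs.** This is what the words say. The formula then divides up to two thighs per woman by the number of women, and a plain binomial interval treats two thighs of the same woman as independent.
- **Women improved on both thighs.** This is what the tables reused from SAP 7.2 suggest. The formula and interval are then sound, but the row and graph carry the name of a different quantity, and the investigator's Month 9 row is the primary result under another label.

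The two quantities can differ widely in the same data. At Month 9 a pooled investigator figure would stand beside the primary both-thighs rate and could be taken for it. The sponsor says in protocol 2.1 that it intends to use this pilot to start a pivotal study if results are favorable, so the wrong rate could be carried forward.

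**Working it through.** The plan states no expected rate, correlation or precision for this row, so there is no figure to reproduce. From the documents I take about 30 women (protocol 8.11, SAP 4.4), hence up to 60 thighs, and the formula above. Response rates and the within-woman correlation ρ are assumptions, shown over a range. Clopper-Pearson is used wherever an exact interval is given; the plan says only binomial.

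**1. How far the two quantities can differ.** Suppose 42 of 60 thighs are improved (70.0%). Let a women be improved on both thighs, b on one and c on neither, with 2a + b = 42 and a + b + c = 30. The extremes are a = 12, b = 18, c = 0 and a = 21, b = 0, c = 9. The same 70% of thighs therefore goes with 12/30 = 40% to 21/30 = 70% of women improved on both.

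**2. A worked split: 18 on both, 6 on one, 6 on neither.**

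- Women: 18/30 = 60.0%, exact 95% CI 40.6-77.3%.
- Thighs over thighs: (2×18 + 6)/60 = 42/60 = 70.0%, plain exact CI 56.8-81.2% (24.4 points wide).
- Thighs over subjects, as the formula reads: 42/30 = 140%.

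**3. Effect of pairing on the interval, if thighs are pooled.** With two thighs per woman the variance is multiplied by 1 + ρ, so the binomial standard error is too small by √(1 + ρ): √1.5 = 1.22 at ρ = 0.5 and √1.9 = 1.38 at ρ = 0.9. In the split above, ρ = (18/30 − 0.70²)/(0.70×0.30) = 0.11/0.21 = 0.52.

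For true coverage I enumerated all outcomes of 30 pairs with thigh rate p, using P(both) = p² + ρp(1−p), P(one) = 2p(1−p)(1−ρ), and the remainder for neither. Three nominal 95% intervals were compared: plain exact on 60 thighs; a t interval on woman-level means; and an exact interval on the effective sample size n* = 60/(1 + r), with r the correlation estimated as above and held between 0 and 1. Coverage over p = 50, 60, 70, 80 and 90%:

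| ρ (assumed) | Plain exact, n = 60 | t interval | Exact on n* |
|---|---|---|---|
| 0 | 96.5-97.3% | 93.0-95.2% | 96.9-97.4% |
| 0.3 | 93.5-94.7% | 92.2-94.8% | 96.0-96.6% |
| 0.5 | 91.4-92.8% | 91.4-94.9% | 95.6-96.4% |
| 0.9 | 87.1-89.2% | 93.7-95.0% | 96.3-97.0% |

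The t interval is not a safe replacement. At p = 90% it covers 92.2% at ρ = 0.3 and 91.4% at ρ = 0.5, below the plain exact interval's 94.5% and 92.5%. It also has zero width if every woman improves on both thighs.

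**4. Which reading the text supports.**

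- *For women:* SAP 7.3.1 reuses the 7.2 tables, which have a Both category and a subject-level responder, and the denominator in SAP 5.6 is subjects.
- *For thighs:* protocol 8.5.1 speaks of improved subjects, and 8.5.2 switches to improved thighs and drops the both-thighs condition. SAP 7.2 graphs responders, and 7.3.1 announces a further graph, of thighs. Month 9 is listed for the combined row, although on the subject reading the investigator's figure there would only repeat the primary result.

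The text does not settle it.

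**The case against.** The strongest reply is that SAP 7.2 makes the meaning plain. Its responder is a subject, its table is Left, Right and Both, and 7.3.1 says that those tables are reused, so a programmer would fill the Both row with women improved on both thighs. Row labels belong in the table shells, a separate document cited in SAP 12 and not available here. A rate above 100% would be noticed at once. No decision depends on the row: SAP 7.3 says that secondary results are interpreted descriptively, and the endpoints in SAP 3.2.3 are per thigh.

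Much of this stands. It limits the point to a minor one, and nothing can be said about the programmed output. It does not remove the point, because the reply itself concedes that the label is wrong, and the change of unit between adjacent sections fits an intended pooled summary about as well.

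Two stronger readings are tempting. A reader might infer that the subject-level meaning is certain, so that the graph in 7.3.1 duplicates the one in 7.2 and should go. The evidence in step 4 does not support that, and deleting the graph could remove an intended summary. A reader might also infer that the GAIS intervals in general are invalid. They are not. Each woman contributes one left and one right thigh, so the separate left and right rates have a correct denominator and independent observations, and the primary rate is defined per subject.

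**Conclusion.** The point holds as a minor defect of definition. The combined row and graph name thighs, the formula divides by subjects, and the unit is not stated. Under the pooled reading, the formula is unusable and the plain interval under-covers by about 2 to 4 points at ρ = 0.5 and 6 to 8 points at ρ = 0.9. At ρ of 0.3 or below there is little or no shortfall. Under the subject reading, only the label is wrong, and the investigator's Month 9 row repeats the primary result.

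These coverage figures assume 30 women with both thighs assessed, thigh response rates of 50-90%, and correlations that the documents do not give. The primary endpoint, its interval and the per-thigh secondary endpoints are unaffected.

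**What to change.** In protocol 8.5.2 and SAP 7.3.1, state the unit of the combined row and, in the SAP, of the graph.

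- **If the unit is the woman:** relabel both as the proportion of subjects at least improved on both thighs, over subjects reporting at the visit. Keep the binomial interval.
- **If the unit is the thigh:** divide by thighs assessed. Give a Clopper-Pearson interval on the effective sample size, n* = thighs/(1 + r) when both thighs are assessed, with r estimated from the data and held between 0 and 1. Set r = 1 when all thighs have the same result; if all 30 women improve on both, this gives n* = 30 and a lower limit of 0.025^(1/30) = 88.4%. Do not use the t interval. Label the row clearly apart from the primary result.

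In protocol 8.4 and SAP 5.6, limit the option of counting thighs over subjects to the separate left and right rates. Drop a graph only if the sponsor confirms that it is a duplicate.

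The cost is a sentence in each of four sections, a row label and a graph title. No new data are needed. If thighs are pooled, the interval widens. In the worked split, n* = 60/1.524 = 39.4 and the interval becomes 53.3-83.5%, 30.2 points wide instead of 24.4. At a true 70% rate, the mean width rises from about 24 points to 27.3, 29.4 and 33.2 points at ρ = 0.3, 0.5 and 0.9.

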8.1 Adverse Events

All adverse events (AEs) will be assigned to a PT and will be classified by Primary SOC according to MedDRA version 24.1 or later.

Any AE which started at or after the first administration of study treatment will be considered as Treatment Emergent Adverse Event (TEAE). If the start date is missing for an AE, the AE will be considered to be treatment emergent. Missing classifications concerning study treatment relationship will also be considered as treatment-related.

A summary of all AEs, will be provided, which will include:

- Number of subjects with at least one AE and number of events (in total as well as serious AEs)
- Number of subjects with at least one related AE and number of events (in total as well as serious AEs)
- Number of subjects with at least one unrelated AE and number of events (in total as well as serious AEs)
- Number of subjects who did not have an AE

The number of subjects with AEs related to study product or injection procedure as well as the number of events will be summarized by SOC, PT, and maximum intensity. In addition, for related AEs the number of days to onset and the duration of event will be summarized by SOC and PT. Action taken for related AEs will also be summarized. Serious AEs will be listed as well as related AEs with late onset (>21 days after most recent treatment).

Non-related AEs will be summarized by SOC, PT, and maximum intensity.

Events that occurred before the first administration of study treatment are included as Medical History.

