#### 8.4 Data Transformations

Responder rate (%) regarding GAIS will be calculated as (number of subjects (or thighs) being at least improved/number of subjects reporting at the specified visit)\*100.

Time to onset of an AE will be derived as the start date minus the date of most recent treatment. If the start date is missing, it will be assumed that the AE started on the day of most recent treatment.

Duration of an AE will be derived as the stop date minus the start date + 1. If the start date is missing, it will be assumed that the AE started on the day of most recent treatment. Missing stop date will not be imputed and therefore no duration will be calculated in these cases. Instead, the number of AEs that were ongoing at the end of the study will be given.

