5.9 Missing Data

As a general principle, no substitutions will be made for missing data. All analyses will be based on available data. Exceptions are the start and stop dates of AEs and therapies (described below). The imputed dates will be used to determine whether an AE is treatmentemergent and whether a therapy is prior or concomitant. Listings of AEs and therapies will present the actual partial dates; imputed dates will not be shown.

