5.9.1 Imputation of Adverse Event Start and Stop Dates

Start date:

- If start date is completely missing, start date is set to date of most recent treatment.
- If (1) year is present and month and day are missing or (2) year and day are present and month is missing:
 - If year = year of most recent treatment, then set month and day to month and day of most recent treatment.
 - If year < year of most recent treatment, then set month and day to December 31st.
 - If year > year of most recent treatment, then set month and day to January 1st.
- If month and year are present and day is missing:
 - If year = year of first dose and
 - If month = month of most recent treatment, then set day to day of most recent treatment.
 - If month < month of most recent treatment, then set day to last day of month.
 - If month > month of most recent treatment, then set day to 1st day of month.
 - If year < year of most recent treatment, then set day to last day of month.
 - If year > year of most recent treatment, then set day to 1st day of month.

Stop date:

If the outcome of the AE was ongoing or unknown, then the rules outlined below will not be applied.

- If stop date is completely missing, stop date is set to date of study discontinuation/end of study date.
- If (1) year is present and month and day are missing or (2) year and day are present and month is missing:
 - If year = year of study discontinuation, then set month and day to month and day of study discontinuation.
 - If year < year of study discontinuation, then set month and day to December 31st.
 - If year > year of study discontinuation, then set month and day to December 31st.
- If month and year are present and day is missing:
 - If year = year of study discontinuation/end of study date and

- If month = month of study discontinuation/end of study date, then set day to day of study discontinuation date.
- If month < month of study discontinuation/end of study date, then set day to last day of month.
- If month > month of study discontinuation/end of study date, then set day to 1st day of month.
- If year < year of study discontinuation/end of study date, then set day to last day of month.If year > year of study discontinuation/end of study date, then set day to 1st day of month.

5.9.2 Imputation of Prior and Concomitant Therapies Start and Stop Dates Start date:

- If start date is completely missing, start date will be imputed with the informed consent date.

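### Some delayed related AEs are timed as early and miss the late-onset listing: those that start 0-21 days after a later session, and those with no start date

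*SAP*

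**What the plan says.** Protocol 8.4 states: "Time to onset of an AE will be derived as the start date minus the date of most recent treatment". SAP 5.6 repeats the rule. SAP 8.1 uses the same starting point for its late-onset display: "Serious AEs will be listed as well as related AEs with late onset (>21 days after most recent treatment".

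For missing dates, SAP 5.6 says: "If the start date is missing, it will be assumed that the AE started on the day of most recent treatment". SAP 5.9.1 agrees: "If start date is completely missing, start date is set to date of most recent treatment". Protocol 8.7 allows this imputation for both time to onset and duration. SAP 5.9 names a different use: "The imputed dates will be used to determine whether an AE is treatmentemergent and whether a therapy is prior or concomitant".

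SAP 6.7 allows up to three sessions at intervals of one month plus up to two weeks, and the protocol's Schedule of Assessments defines a month as four weeks. Protocol 7.2.5.3 lists the AE fields. They include the start date and the relation to product or procedure, but not the session suspected.

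**The concern.** Time to onset is part of the first safety endpoint. A clock that restarts at each session treats the latest injection as the origin of every AE. When sessions are 28 to 42 days apart and late means more than 21 days, a slow reaction to one session can surface shortly after the next and be counted as prompt. For example, with sessions on days 0, 28 and 56, a session-1 reaction that starts on day 30 is recorded with an onset of 2 days.

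An undated AE has a related problem: its onset is set to 0, a value nobody observed, and that value enters the summaries. Both rules can only move recorded onset earlier than the true latency.

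This matters because Protocol 2.3 names papules, nodules and mass or induration among the most common AEs, and the diary (Protocol 7.2.1) does not ask about them by name. Their timing therefore rests mainly on the AE onset rules. Protocol 2.1 says the sponsor intends to use the pilot to start a pivotal study if results are favorable, so the onset profile may be carried forward.

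**Working it through.** The plan gives no figure on this point, so there is none to reproduce. The check counts days.

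**Inputs**
- Sessions s1, s2, s3, spaced 28 to 42 days apart (SAP 6.7; Schedule of Assessments).
- Late means more than 21 days after the most recent treatment, related AEs only (SAP 8.1).
- End of follow-up: Month 12 = 12 × 28 = day 336, with a window of ±14 days, so 322 to 350 (Protocol 4.5.10).
- Assumptions: three sessions are given, and an AE that starts on a treatment day counts as day 0 after that session.

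**Formula.** For an onset on day t, recorded onset r(t) = t − (latest session day on or before t). The AE is listed if r(t) > 21. A reaction to session j is masked if t − s_j > 21 but r(t) ≤ 21.

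**Session 1, sessions on days 0, 28, 56**
- Possible late onset days: 22 to 336 = 315.
- Masked: days 28-49 (22 days) and 56-77 (22 days) = 44.
- 44/315 = 14.0%. Ending follow-up on day 350 or day 322 gives 44/329 = 13.4% or 44/301 = 14.6%.
- The count of 44 is the same at every allowed spacing.

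**Session 2**
- Possible late onset days: 50 to 336 = 287. Masked: 56-77 = 22.
- 22/287 = 7.7%. Over all schedules and end dates the range is 7.3% to 8.5%.

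**Session 3:** nothing is masked.

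**Fewer sessions:** with two sessions, 22 of 315 session-1 days are masked (7.0%); with one session, none.

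**Where the loss sits.** From day 22 to 21 days after session 3, the masked share is 44 of 56 days (78.6%) at 28-day spacing and 44 of 84 (52.4%) at 42-day spacing. After that, every onset with a known date is listed.

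**Wholly missing start date.** Start = treatment day, so recorded onset = 0. Since 0 ≤ 21, no such AE can be listed as late. For these AEs the most recent treatment is itself undefined: it could be the last session before the report or the last session received.

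**Partial dates.** SAP 5.9.1 has two rules that also give onset 0: "If month = month of most recent treatment, then set day to day of most recent treatment" and "If year = year of most recent treatment, then set month and day to month and day of most recent treatment". Another does not: "If month > month of most recent treatment, then set day to 1st day of month". Assume treatment dates spread evenly over a year, equally weighted latencies and no later session. If only the day is missing, 37.7% of true latencies of 22-60 days become 21 or less (96.7% at 22 days, 37.5% at 40, none from 52). If only the year is known, 64.4% of latencies of 22-280 days do. The SAP does not say whether these partial-date rules feed the onset statistics, so this is a side result only.

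**Check of a simple alternative.** Counted from first treatment, all 315 onset days exceed 21, against 315 − 44 = 271 under the SAP rule. The 44 days gained are also the days on which prompt reactions to sessions 2 and 3 start. That starting point used alone would label those prompt reactions late.

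**The case against.** The strongest reply is that the rule is prespecified, consistent between the documents and defensible. After repeat injections the causal session is not observed, so true latency is unknown, and Protocol 4.2 says most AEs arise within two to three weeks of a session. This stands as a reason to keep the most recent treatment as the main anchor. It is no reason to show only that anchor.

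Several stronger readings are tempting, and the documents do not support them:

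- **Delayed reactions in general drop out.** They do not. Known onsets more than 21 days after the last session are always listed, which covers most of follow-up. Sessions 2 and 3 are optional (Protocol Figure 1), so some subjects may have little or no masking.
- **The late-onset listing is the only view of delayed reactions.** Onset is also summarised by SOC and PT for related AEs, with minimum and maximum (Protocol 8.6). Dated listings carry a relative study day (SAP 5.1), AE listings show the actual partial dates (SAP 5.9), and serious AEs are listed whatever their onset. Relative study day is not defined, however, and the table shells are a separate document.
- **A quarter to a third of late reactions are lost.** That needs an assumed latency. If latency is uniform on 22-90 days (69 values) and reactions come equally from three sessions, the masked share is (44 + 22 + 0)/207 = 31.9% at 28-day spacing and (29 + 22 + 0)/207 = 24.6% at 42-day spacing. If latency runs evenly to Month 12, it is (14.0 + 7.7 + 0)/3 = 7.2%. The documents favor neither.
- **SAP 5.9 contradicts SAP 5.6.** SAP 5.9 names a use of imputed dates without excluding others, and Protocol 8.7 permits the use for onset and duration. The wording could be clearer, but the reading as a contradiction is weak.
- **Undated AEs are mostly gradual ones.** Nothing says so. Start date is a required field and AEs are asked about at every visit and call, so wholly missing dates should be few.

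It is also fair to say that masked AEs stay in the related-AE tables, that counting undated AEs as treatment-emergent is conservative, and that dating them to the treatment day tends to lengthen duration.

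**Conclusion.** The point holds in a limited form. Two groups of related AEs can be recorded as early and miss the late-onset listing: reactions to session 1 or 2 that start 0-21 days after a later session, and all AEs with a wholly missing start date.

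Over follow-up to day 336 with three sessions, the first group covers 14.0% of possible session-1 onset days and, at 28-day spacing, 7.7% of those for session 2. The loss is concentrated in the treatment period and the three weeks after it. These shares rest on three sessions being given and describe days, so they are not event rates. The number of AEs affected cannot be derived: the documents give no latency distribution, no expected rate of missing dates and no field for the suspected session.

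The bias runs in one direction and touches part of a safety endpoint. It does not affect AE incidence or the effectiveness analysis. In a descriptive pilot this is a worthwhile, inexpensive improvement and no obstacle to the plan.

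**What to change.** Amend SAP 5.6 and 8.1, and align Protocol 8.4 and 8.7:

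1. Keep onset from the most recent treatment as the main measure. Add days since first treatment and days since each session received.
2. Keep the listing of related AEs with onset more than 21 days after the most recent treatment. Beside it, as a separately marked group, list related AEs that start within 21 days of session 2 or 3 but more than 21 days after an earlier session.
3. For a wholly missing start date, use the imputed date only to set treatment-emergent status. Leave these AEs out of the onset and duration statistics, state how many there are, and show them as onset unknown beside the late-onset listing.

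The cost is extra columns, a longer listing, and slightly fewer events in the onset and duration summaries. Because sessions are at least 28 days apart, any onset after session 2 is already more than 21 days after session 1. The marked group will therefore also hold the prompt reactions to sessions 2 and 3 that are reported as related AEs. That is why it must stay separate from the main late-onset listing. With about 30 subjects it can be read case by case, and no new data need to be collected.
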